5.5.2 DESCRIPTIVE STATISTICS

TPL/008/2(v1.0)

DOMINO-HD: STATISTICAL ANALYSIS PLAN

Categorical data will be presented using frequencies and percentages. Continuous data will be presented using number of patients, mean and SD or median and IQR to summarise the key demographics and patient characteristics. Baseline data will be tabulated for each site, and in total. Baseline data for those who were followed up at 12 months will also be tabulated and compared to those who were not followed up at 12 months. Summary statistics and percentage of missing values will be tabulated and reported for all covariates listed in Table 1 (baseline measures).

6. ANALYSIS

6.1 OUTCOME DEFINITIONS

6.1.1 PRIMARY OUTCOME(S)

The primary objective of this study is to establish the feasibility of linking lifestyle, clinical and genetic data and to explore their interplay with HD symptoms and severity.

We will explore the proportions of recruited participants with linked DOMINO-HD and Enroll-HD clinical data as well as linked GWAS data. We will also explore follow-up rates and lifestyle and wearable activity tracker data completeness and balance statistics in important variables. Our data will be used to provide progression criteria recommendations for future studies in this field.

Aspects of feasibility which will be assessed are:

- Completeness of key lifestyle questionnaires (at baseline: HD Pro-Triad, FFQ, LTPA, Sleep, IPAQ, Relationship) data [>80% returned with >80% completeness = feasible, >60% returned with >60% completeness = changes required, <60% returned or <60% completeness = not feasible]
- Completeness of activity tracker data [>70% feasible, 50-70% changes required, <50% not feasible]
- % participants linked with Enroll-HD clinical data [>80% feasible, 60-80% changes required, <60% not feasible]
- % participants linked with GWAS data [>60% feasible, 40-60% changes required, <40% not feasible]
- % participants with follow-up at 12m [>70% feasible, 50-70% changes required, <50% not feasible]
- Feasibility of balancing important covariates. Adequate balance of baseline covariates is achieved when the maximum Kolmogorov-Smirnov (KS) value is equal to or below 0.1. However, as the recommendation is for 60-80 observations per covariate per treatment

TPL/008/2(v1.0)

Centre for Trials Research Canolfan

Ymchwil Treialon

DOMINO-HD: STATISTICAL ANALYSIS PLAN

group (Markoulidakis, Holmans, et al., 2021), the feasibility of achieving balance should be determined alongside the available sample size.

• Agreement between questionnaire and activity tracker data

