2.2 OBJECTIVES

The primary objective (and the focus of this statistical analysis plan) is to establish the feasibility of linking lifestyle factors and genetic risk factors to explore their interplay with HD symptom progression and severity.

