6.1.2 TIMING, UNITS AND DERIVATION OF PRIMARY

The primary outcomes will be assessed at 12-months follow-up.

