We will derive a Mediterranean Diet Index (MDI) as defined by (Trichopoulou et al., 2003). This index's values range from 0 to 9, with higher values indicating higher adherence to an MD. The final score is the sum of nine elements, each of which is either 0 or 1. Beneficial components (namely 1. vegetables, 2. legumes, 3. fruits and nuts, 4. cereal, and 5. fish) contribute one point if their consumption is above the sex-specific sample median. For non-beneficial components, (6. dairy, 7. meat and poultry) one point is assigned to those whose consumption is below the sex-specific sample median. Finally, for alcohol consumption (8.), one point is assigned to men who consume between 10 and 50 g per day and to women who consume between 5 and 25 g a day. Finally, to score lipid intake, the unsaturated to saturated fatty acids (9.) ratio is calculated and one point assigned if the ratio exceeds the sex-specific sample median. A full description of the definition of the MDI is in Appendix A.

Additionally, the Healthy Eating Index (HEI) will be used as a diet score. Its values range from 0 to 100, with higher values representing better eating habits. The final score is a sum of 13 components, nine categories of adequate eating, and four moderators. A full description of the definition of the HEI is in Appendix B.

Both MDI and HEI will be used (one at a time) to assess the sensitivity of our findings. Additionally, the two scores will be compared as to their effect on the progression of HD – unless one is dropped (see section 6.2.3).

3. Physical activity:

Step counts over a 6-week period from the baseline assessment will be extracted from each participant's FitBit. 5000 steps per day (Tudor-Locke et al., 2013) will be used as a threshold to dichotomise participants into sedentary (< 5000 steps per day) and active (\geq 5000 steps per day).

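### SAP 6.1.1 judges five feasibility percentages one at a time and never counts the participants who hold the linked data types together, although linking them is the primary objective

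*SAP*

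**What the plan says.** SAP 2.2 gives the primary objective as to "establish the feasibility of linking lifestyle factors and genetic risk factors" and to explore their interplay with progression and severity. Section 6.1.1 restates it as to "establish the feasibility of linking lifestyle, clinical and genetic data and to explore their interplay with HD symptoms and severity".

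Section 6.1.1 then lists seven aspects of feasibility. Five are percentages with cut-offs:
- baseline questionnaires: ">80% returned with >80% completeness = feasible";
- activity tracker completeness: above 70%;
- Enroll-HD linkage: "participants linked with Enroll-HD clinical data [>80% feasible, 60-80% changes required, <60% not feasible";
- genetic linkage: "participants linked with GWAS data [>60% feasible, 40-60% changes required, <40% not feasible";
- 12-month follow-up: above 70%.

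The sixth is covariate balance, a maximum Kolmogorov-Smirnov statistic of at most 0.1. It is to be read with the available sample size because "the recommendation is for 60-80 observations per covariate per treatment" group. The seventh is agreement between questionnaire and tracker data, with no threshold.

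Section 6.2.1 reports the criteria in a table, one by one. The SAP gives no rule for combining them.

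**The concern.** Linkage is a property of the individual: the same person must have lifestyle, clinical and genetic data. A set of marginal percentages does not determine how many such people there are, because that depends on whether the gaps fall in the same participants or in different ones. The SAP neither states an expected overlap nor asks for it to be measured against a criterion.

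The feasibility table is the primary result, and section 6.1.1 says the data will inform progression criteria for later studies. A later study that adopted these thresholds would have no assurance that meeting them yields a usable linked dataset.

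A related gap is that the tracker criterion names no time window, and the SAP is not consistent on which window defines the exposure. Section 6.2 uses "Step counts over a 6-week period from the baseline assessment", whereas Table 5 defines daily steps as an average over one week. Until this is settled, having tracker data cannot be defined for a joint count.

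**Working it through.** **Plan's own figure.** The SAP gives no joint proportion, so there is none to reproduce. The check is what the five cut-offs imply.

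**Inputs.** From 6.1.1, the feasible limits are questionnaires 0.80, tracker 0.70, Enroll-HD 0.80, GWAS 0.60 and follow-up 0.70. From 3.3, N is 300 to 450. Two assumptions are needed: tracker completeness is a share of participants (6.1.1 does not say whether it means participants, days or hours), and 0.80 is the share of participants with usable questionnaires.

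**Formulas** for k criteria with rates p:
- least overlap: max(0, sum of p − (k − 1));
- independence: product of the p;
- full nesting: the smallest p.

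| Set | Least overlap | Independence | Full nesting |
|---|---|---|---|
| All five | 3.60 − 4 = −0.40, so 0% | 0.80 × 0.70 × 0.80 × 0.60 × 0.70 = 0.188: 56 of 300, 85 of 450 | 60%: 180 of 300, 270 of 450 |
| Four, without GWAS | 3.00 − 3 = 0% | 0.80 × 0.70 × 0.80 × 0.70 = 0.314: 94 of 300, 141 of 450 | 70%: 210 of 300, 315 of 450 |
| Without GWAS, follow-up nested in Enroll-HD linkage | 0.80 + 0.70 + 0.70 − 2 = 20%: 60 of 300, 90 of 450 | 0.80 × 0.70 × 0.70 = 0.392: 118 of 300, 176 of 450 | 70%: 210 of 300, 315 of 450 |

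In the third row the Enroll-HD rate drops out because everyone followed up is already linked.

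**Sensitivity to better rates.** If all five were 90%, the joint share would be 4.5 − 4 = 50% at least, 0.9^5 = 59% under independence and 90% at most.

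**Against the SAP's own size guide.** The guide is 60 to 80 per covariate per group. Section 6.2.2 makes balancing the other two lifestyle factors the primary goal, which implies 120 to 160 per group. Even splits without GWAS give:
- at N = 300: 94/2 = 47, 118/2 = 59 and 210/2 = 105 per group;
- at N = 450: 141/2 ≈ 70, 176/2 = 88 and 315/2 ≈ 158 per group.

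At 300, the independence figures fall short for even one covariate, and full nesting falls short for two. At 450, the independence figures suffice for one covariate but not two, and full nesting is within the range for two.

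**Against the stated detectable effect.** Section 3.3 gives 0.23 at N = 300. If the loss from weighting is proportionally the same in a subset, this scales as 0.23 × √(300/n): 0.41 for n = 94, 0.37 for n = 118 and 0.27 for n = 210. This shows what subset size costs. It is not a forecast of the planned analyses.

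**The case against.** **The balance item already guards against small numbers.** This stands in part. It is not a percentage, and it tells the analyst to weigh the available sample. It is therefore wrong to say that every criterion is a percentage, or that all seven could read feasible however few people are linked. But the item sets no number for the linked set and does not cover GWAS linkage or follow-up.

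**Independence is a poor central case.** This also stands in part. Under 2.1.1 every participant must consent to Enroll-HD, and 5.4.1 ties the 12-month visit to the Enroll-HD protocol, so follow-up is plausibly nested in Enroll-HD linkage. That raises the four-part share from 31% to 39%. The range remains wide.

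**The fully complete set is not the analysis set.** This is correct. cUHDRS is a secondary outcome, 4.3 includes everyone with outcome data, 6.3 plans to attempt multiple imputation, and 6.2.2 uses genetic data only if the sample allows. These soften the effect on the lifestyle analyses. They do not answer the primary question of whether linkage was achieved.

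**The opening of 6.1.1 already promises linked proportions.** It says that proportions with linked DOMINO-HD and Enroll-HD data, and with linked GWAS data, will be explored. No cut-off or row in the table follows from that sentence, and it leaves out 12-month follow-up.

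**Timing.** A reader might see a contradiction between baseline questionnaires and the statement that "The primary outcomes will be assessed at 12-months follow-up". The documents do not support that: counting baseline returns at the end of the study is consistent. Nor does it follow that one linked visit would pass as adequate clinical data, because 12-month follow-up has its own criterion. Judging tracker wear beyond the exposure window is also legitimate, since 3.1 describes 12 months of lifestyle exposure.

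**Conclusion.** The point holds for the five percentage criteria. Applied exactly as written, the plan can return five feasible verdicts while the share of participants with everything lies anywhere from 0% to 60%, or 0% to 70% without GWAS. Those figures rest on rates at the limits, on tracker completeness being a share of participants, and on overlap that the SAP does not state. Higher observed rates narrow the gap considerably.

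Three stronger readings are not supported. The documents do not show that few participants will be linked; with well-nested data most could be. They do not show that the criteria use different denominators: three are worded as percentages of participants, and only the tracker's unit is undefined. And a linked set below the 60 to 80 guide is not inevitable, as the splits at 450 show.

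This is a gap in how the primary result is summarised, worth closing before the data are seen. It does not invalidate the individual criteria, which remain useful for showing where data are lost.

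**What to change.** 1. Reconcile the tracker exposure window between 6.2 (six weeks, for steps) and Table 5 (one week, for steps and sleep). State the unit and window of the tracker criterion, and report longer-term wear separately.
2. Add one row to the feasibility table in 6.2.1, defined in 6.1.1, with all consented participants as denominator. Count a participant who has the required baseline questionnaires, tracker data in the exposure window, and all four cUHDRS components at both baseline and 12 months. Show the row with and without GWAS.
3. Name the required questionnaires. Leave out the LTPAQ, which 5.5.1 makes optional although 6.1.1 lists it among the key questionnaires.
4. Report the joint figure beside the single criteria and take it into account in the feasibility conclusion and the progression recommendations. If it is to carry a cut-off, set it before the data are seen.

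The cost is some SAP wording and one table row from data already held. The downside is presentational: the joint figure cannot exceed the lowest single percentage on the same denominator and will usually be lower.

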6.1.2 TIMING, UNITS AND DERIVATION OF PRIMARY

The primary outcomes will be assessed at 12-months follow-up.

6.1.3 LIST OF SECONDARY OUTCOMES

We will use a clinical composite score for the initial secondary analyses, namely the composite Unified Huntington's Disease Rating Scale (cUHDRS) defined by (Schobel et al., 2017) as follows:

$$cUHDRS = \frac{TFC - 10.4}{1.9} - \frac{TMS - 29.7}{14.9} + \frac{SDMT - 28.4}{11.3} + \frac{SWRT - 66.1}{20.1} + 10$$

where:

- Total Functional Capacity (TFC) is a standard assessment of overall function in HD and ranges from 13 (normal function) to 0 (complete loss of function).
- The Total Motor Score (TMS) has a maximum score of 124. Higher values indicate more severe impairment.
- SDMT is the Symbol Digit Modality Test. Higher scores reflect better cognitive functioning.
- SWRT is the Stroop Word Reading Test. Higher scores reflect better cognitive functioning.

The higher the value of cUHDRS, the better the condition of the patient (lower severity). As the disease progresses and the condition of the individual becomes more severe, the cUHDRS drops.

Individual components of cUDHRS (namely TFC, TMS, SDMT and SWRT) will also explored. This means that the entire analysis described below for the cUHDRS as an outcome will be reproduced for each of the four cUHDRS components (one at a time).

6.1.4 ORDER OF TESTING

TPL/008/2(v1.0)

Not applicable.

6.1.5 TIMING, UNITS AND DERIVATION OF SECONDARIES

The secondary outcomes (cUHDRS, TMS, TFC, SWRT and SDMT) will be assessed 12 months after the initial (baseline) assessment.

6.2 ANALYSIS METHODS

The main modifiable lifestyle factors we are interested in, in terms of their impact on cUHDRS progression, are sleep, diet, and physical activity.

1. Sleep:

Total minutes of sleep are available per participant through the extracts from activity trackers. As there is no evidence in the literature about the minimal time of sleep required for individuals with HD, we will utilise the first tertile to dichotomise the participants into two categories (those with more sleep than two thirds of the sample vs. the rest). Dichotomisation based on the first quartile and the median, respectively, will be used as an alternative, to assess the sensitivity of our findings. Sleep efficiency – defined as the ratio of sleep duration (average total sleep time, TST) to duration in bed (average total time in bed, TBT) – will also be considered. TBT and TST will be extracted from FitBit. Alternatively, propensity score (PS) weighting for continuous treatment variables, as described in section 6.2.2, could be explored. The first tertile will be used as a cut-off point for the primary analysis, dichotomisation on the first quartile and the median, respectively, will also be explored, to understand the sensitivity of our findings.

The HD sleep questionnaire contains 45 questions that focus on different sleep-related issues such as duration, quality of sleep, abnormal nocturnal behaviour and quality of life. Variables emerging from the HD sleep questionnaire will be reported descriptively. A sleep disturbance score will be derived from a sub-set of the questions, namely 4-11, 14, 15, 18, 19, 14, 27, 28, 34 (Goodman et al., 2010).

Self-reported total sleep time (calculated from questions 1 and 2 of the HD sleep questionnaire) will be compared with average total sleep time from activity trackers. The values for sleep efficiency from activity trackers and sleep questionnaires (sleep disturbance) will also be assessed for correlation (association of high sleep disturbance with low sleep efficiency) and reported.

2. *Diet*:

TPL/008/2(v1.0)

DOMINO-HD:	STATISTICAL ANALYSIS PLAN
------------	---------------------------

We will derive a Mediterranean Diet Index (MDI) as defined by (Trichopoulou et al., 2003). This index's values range from 0 to 9, with higher values indicating higher adherence to an MD. The final score is the sum of nine elements, each of which is either 0 or 1. Beneficial components (namely 1. vegetables, 2. legumes, 3. fruits and nuts, 4. cereal, and 5. fish) contribute one point if their consumption is above the sex-specific sample median. For non-beneficial components, (6. dairy, 7. meat and poultry) one point is assigned to those whose consumption is below the sex-specific sample median. Finally, for alcohol consumption (8.), one point is assigned to men who consume between 10 and 50 g per day and to women who consume between 5 and 25 g a day. Finally, to score lipid intake, the unsaturated to saturated fatty acids (9.) ratio is calculated and one point assigned if the ratio exceeds the sex-specific sample median. A full description of the definition of the MDI is in Appendix A.

Additionally, the Healthy Eating Index (HEI) will be used as a diet score. Its values range from 0 to 100, with higher values representing better eating habits. The final score is a sum of 13 components, nine categories of adequate eating, and four moderators. A full description of the definition of the HEI is in Appendix B.

Both MDI and HEI will be used (one at a time) to assess the sensitivity of our findings. Additionally, the two scores will be compared as to their effect on the progression of HD – unless one is dropped (see section 6.2.3).

3. Physical activity:

Step counts over a 6-week period from the baseline assessment will be extracted from each participant's FitBit. 5000 steps per day (Tudor-Locke et al., 2013) will be used as a threshold to dichotomise participants into sedentary (< 5000 steps per day) and active (\geq 5000 steps per day).

A MET-minute is the amount of energy expended during a minute while at rest. It is a ratio of a person's working metabolic rate relative to their resting metabolic rate (one MET is the energy spent sitting at rest for one minute). As there is no evidence in the literature about a clear distinction between active and inactive lifestyle for individuals with HD, participants in the lowest tertile (\leq 33%) will be classified as inactive (Schiepers et al., 2018). MET-minutes will be extracted from FitBit. MET-minutes will be used as an alternative measure of physical activity (if available) to assess the sensitivity of our findings.

Construction of LifeHD score:

A LIBRA style index (Anstey et al., 2013; Kivipelto et al., 2006; Schiepers et al., 2018) will be created to investigate the association of a lifestyle-based score with the progression of HD

TPL/008/2(v1.0)

DOMINO-HD: STATISTICAL ANALYSIS PLAN

(as measured by cUHDRS and its four components). This will be called LifeHD. Modifiable lifestyle factors will be included, namely:

- Sleep;
- Diet;
- Physical activity;
- BMI.

Additionally, the following non-modifiable measures will be included:

- Age group (< 47yrs, 47 53yrs, > 53yrs);
- CAG repeat length;
- HD stage.

To achieve the scoring sums (LifeHD scores), the steps in Appendix C will be followed.

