6.2.2 COVARIATE ADJUSTMENT

Unweighted analyses (using regression models) will control for age, HD stage, as well as baseline values for the outcomes. Additionally, we will control for the two lifestyle (the continuous version of these) factors not included in each case.

The primary goal is to control for confounding bias, using PS and balancing weights (Markoulidakis, Taiyari, et al., 2021), for the two lifestyle factors other than the one under study in each case. Expecting limitations due to the restricted sample size (Markoulidakis, Holmans, et al., 2021), we will attempt to balance additionally for age, HD stage, and baseline values of the outcome.

The outcome analysis will also be performed using the LifeHD score constructed, as a categorical covariate, with and without the use of PS and balancing weights. The LifeHD score will be used both in addition to the individual lifestyle factors (e.g. using LifeHD score as 'treatment', and the three lifestyle factors as confounders), and solely – without taking into consideration the other lifestyle factors.

Outcome will be standardised, so that we report standardised effect sizes. The estimand of interest (e.g. ATE or ATT) will be determined based on whether adequate balance is achieved or not. If we are unable to achieve adequate balance, then unweighted regression and means difference will be reported.

Additionally, significance tests for difference of means of the covariates we wish to control for and the outcome will be reported. The pseudo-groups will be created using the binary indicators of diet, sleep, and physical activity.

Genetic information (via polygenic risk scores) will only be used in the analysis if it is feasible based on the available sample.

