Appendix C: LifeHD score

Table 4 reports the covariates which will be included in the LifeHD index. The following algorithm describes the development of the score.

- Step 1. The risk factors will first be included separately in a regression model (together with non-lifestyle factors: age, sex, HD stage, time since diagnosis, and follow-up time since last visit). We will use a linear or logistic regression model, depending on the outcome (continuous or binary). This will also enable us to understand the impact of each category on the outcome variable and define the reference category for each factor. For diet, the sign and magnitude of each category will allow us to understand the most and least beneficial clusters thus the beneficial category is group 1, and the other category is 0. The least beneficial cluster will be the reference category to another (group 1 or higher for more than two categories) will increase the index thus, higher values of the index indicate "better" lifestyle.
- Step 2. Factors that were significant in the first step will be simultaneously placed into a single regression model linear or logistic regression depending on the outcome. (For DOMINO-HD, as the outcome is cUHDRS or its components linear regression will be used.)
- Step 3. From the final regression models of step 2, risk scores will be assigned for each factor with the respective β coefficients (steps 4 and 5).
- Step 4. All β coefficients will be standardised so that the lowest one has a value of 1 this is achieved by multiplying every β coefficient with 1/minimum(β).

TPL/008/2(v1.0)

DOMINO-HD: STATISTICAL ANALYSIS PLAN

Step 4b.	(optional) Rounding each coefficient to the closest integer. In this case,
	all individual scores are positive integers. This will enable easier
	calculaiton of the scores, and higher values of the score would indicate
	better "lifestyle".

Step 5. The risk score for an individual will be obtained by summing the scores for the appropriate level of each of the risk factors.

Correlation and association of LifeHD with the outcome and the lifestyle factors under study (diet, sleep, physical activity) will be tabulated.

Variable	Calibration
Diet*	MDI: 0-5; 6-9
	HEI: 0-59; 60-100
Sleep*	SE > tertile/quantile
	$SE \leq tertile/quantile$
Physical activity*	MET > tertile
	$MET \leq tertile$
BMI*	$BMI \le 25 \text{ normal}$
	$25 < BMI \le 30$ overweight
	BMI > 30 obese
Age**	< 47 years old
	47 – 53 years old
	\geq 53 years old

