CAG repeat length**	35 < CAG < 42
	$CAG \ge 42$

Table 4: Lifestyle factors included in LifeHD. *Modifiable; **Non-modifiable

TPL/008/2(v1.0)

Canolfan Ymchwil Treialon

DOMINO-HD: STATISTICAL ANALYSIS PLAN

HD stage**	Participants could be either in stage:	
	- Late pre-manifest (LPM): No motor onset, age \geq 18yrs, CAG \geq 36, CAP $>$ 80	
	- Stage 1: 10 < TFC ≤ 13	
	- Stage 2: 6 < TFC ≤ 10	
	- Stage 3: TFC ≤ 6	
Antidepressant	Use; or	
medication*	No use	

Canolfan **Ymchwil Treialon**

DOMINO-HD:	STATISTICAL ANALYSIS PLAN	

Table 5: Definition of variables/outcomes

Outcome/definition	Scale(s)	Timingofmeasurements	Score range	Interpretation
	Age	At baseline		The age of the participant at the time of the baseline assessment
	HD stage	At baseline	LPM, stage 1, 2, 3	The HD stage of the participant at the beginning of the study
	CAG	At baseline		The length of CAG repeat of the participant
	САР	At baseline		The CAP score of the participant at the beginning of the study
	Sex	At baseline		The sex of the participant as specified at birth
Severity of the disease	cUHDRS	At baseline and 12 months after baseline		Measure of the severity of the disease at the baseline assessment

TPL/008/2(v1.0)

Page 30 of 41

CAERDY

Canolfan Ymchwil Treialon

DOMINO-HD: STATISTICAL ANALYSIS PLAN

				and at the time of the follow-up assessment. Higher values indicate less severe impairment.
Severity of the disease – motor	TMS	At baseline and 12 months after baseline	0-124	Lower values indicate less severe impairment
Severity of the disease – functional	TFC	At baseline and 12 months after baseline	0-13	Higher values indicate less severe impairment
Severity of the disease – cognitive	SDMT	At baseline and 12 months after baseline	Raw number of correct answers	Higher values indicate less severe impairment
Severity of the disease – cognitive	SWRT	At baseline and 12 months after baseline	Raw number of correct answers	Higher values indicate less severe impairment
Sleep quality	Total minutes of sleep	At baseline	Time (in minutes)	Average (over one week) minutes of sleep per day
Sleep quality	Sleep efficiency	At baseline		The ratio of total minutes of sleep to time in bed

PRIFYSGOL CAERDYD

Canolfan Ymchwil Treialon

DOMINO-HD: STATISTICAL ANALYSIS PLAN

Adherence to Mediterranean diet	MDI score	At baseline	0-9	Higher values indicate better adherence to Mediterranean diet
Adherence to a healthy diet	HEI score	At baseline	0-100	Higher values indicate healthier diet

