Physical activity	Step count	At baseline	Raw number of steps per day	Average (over one week) number of daily steps
Physical activity	MET-minutes	At baseline		A MET is the ratio of a person's working metabolic rate relative to their resting metabolic rate (one MET is the energy spent sitting at rest). Higher values indicate more active lifestyle.
	BMI	At baseline	Raw number	 ≤ 25 normal 25 < BMI ≤ 30 overweight > 30 obese
Lifestyle undex	LifeHD	At baseline		Higher values indicate a better overall lifestyle (better adherence to

TPL/008/2(v1.0)

Canolfan Ymchwil Treialon

DOMINO-HD:	STATISTICAL ANALYSIS PLAN

				a healthy diet, sleep schedule, and physical activity)
Total FitBit wear time	Total wear hours	Throughout the study	Time (in minutes)	Adherence to wearing the FitBit. Higher values indicate better (more consistent) usage of the tracker.

Canolfan Ymchwil Treialon

DOMINO-HD: STATISTICAL ANALYSIS PLAN

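### LifeHD is read as a lifestyle score, but its sum includes age, CAG length and HD stage, so it will mainly reflect disease stage and may contain no lifestyle item

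*SAP*

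**What the plan says.** Section 6.2 says the index "will be created to investigate the association of a lifestyle-based score with the progression of HD", measured by cUHDRS and its four components. After naming sleep, diet, physical activity and BMI, it continues: "Additionally, the following non-modifiable measures will be included". The three measures are age group, CAG repeat length and HD stage.

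Appendix C gives the algorithm. Each factor is first tested separately. Then "Factors that were significant in the first step will be simultaneously placed into a single regression model". The coefficients are rescaled so that the smallest equals 1, and "The risk score for an individual will be obtained by summing the scores for the appropriate level of each of the risk factors". Nothing separates lifestyle from non-lifestyle items in that sum, and no lifestyle-only version is planned.

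Table 4 defines three of the four HD stages by TFC, for example "Stage 1: 10 < TFC ≤ 13". Late pre-manifest is the exception: it is defined by motor onset, age, CAG and CAP. TFC is one of the four terms of cUHDRS in Section 6.1.3, which adds: "Individual components of cUDHRS (namely TFC, TMS, SDMT and SWRT) will also explored".

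Table 5 interprets LifeHD thus: "Higher values indicate a better overall lifestyle (better adherence to" a healthy diet, sleep schedule and physical activity. Step 1 of Appendix C also equates higher values with a better lifestyle.

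Section 6.2.2 plans the outcome analysis "using the LifeHD score constructed, as a categorical covariate, with and without the use of PS and balancing weights", once with the three lifestyle factors as confounders and once without them.

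**The concern.** A score built to predict the outcome, with disease stage among its ingredients, will give stage much of the weight. Part of the score is then a banded baseline reading of its own outcome. A participant scores high largely by being younger, having a shorter repeat and being at an earlier stage, and the SAP would report this as a better lifestyle.

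Significance selection makes this worse. If the lifestyle items fail the first step and stage passes, the quantity called LifeHD consists of non-lifestyle items only.

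The variant with diet, sleep and activity as confounders has the same problem. Once those three are held fixed, what still varies in LifeHD is stage, age, CAG and BMI, plus antidepressant use if Table 4 is followed. That is mainly non-lifestyle variation.

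Section 2.1 wants these data to inform predictive modelling and the development of interventions, so a mislabelled score could mislead later work.

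**Working it through.** **The only design figure.** Section 3.3 gives a detectable effect of 0.23 at N = 300, 80% power and a 0.05 error rate (taken as two-sided). Without a weighting penalty, (1.960 + 0.842) × √(1/300) = 0.162. A value of 0.23 implies an effective N of (2.802/0.23)² = 148, a design effect of 300/148 = 2.02. The SAP states no design effect, so 0.23 is plausible but cannot be confirmed. It is used below only as a scale for a lifestyle effect.

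**Stage contrasts from TFC alone.** The cUHDRS formula divides TFC by 1.9. Assume band midpoints of 3 (Stage 3), 8.5 (Stage 2) and 12 (Stage 1), and TFC 13 for late pre-manifest. Relative to Stage 3:
- Stage 2: (8.5 − 3)/1.9 = 2.89 points
- Stage 1: (12 − 3)/1.9 = 4.74 points
- Late pre-manifest: (13 − 3)/1.9 = 5.26 points

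**Points after rescaling, if the smallest coefficient is a lifestyle item.** The unit of 0.23 is unclear: Section 3.3 calls it an effect size but also a change in the composite, and Section 6.2.2 standardises the outcome. If the divisors in the cUHDRS formula are SDs (an assumption), four non-negatively correlated unit-SD terms give a cUHDRS SD between 2 and 4. Then 0.23 SD is 0.46 to 0.92 points.

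| Lifestyle coefficient (points) | Stage 2 | Stage 1 | Late pre-manifest |
|---|---|---|---|
| 0.23 (raw points) | 12.6 | 20.6 | 22.9 |
| 0.46 (SD = 2) | 6.3 | 10.3 | 11.4 |
| 0.92 (SD = 4) | 3.1 | 5.1 | 5.7 |

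The lifestyle item scores 1 in each row.

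**Share of score variance.** Stage points of 0, 2.89, 4.74 and 5.26 have variance 4.24 with equal quarters in each stage. With an assumed mix of 10% Stage 3, 20% Stage 2, 40% Stage 1 and 30% late pre-manifest, it is 2.54. Three independent binary lifestyle items with coefficient b contribute b² × (0.21 + 0.222 + 0.25) = 0.682b², assuming splits of 30:70, 1/3:2/3 and 50:50.
- b = 0.23: 0.036, a share of 0.8 to 1.4%
- b = 0.46: 0.144, a share of 3.3 to 5.4%
- b = 0.92: 0.577, a share of 12.0 to 18.5%

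These shares leave out age, CAG, BMI and antidepressant use.

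**Simulation with no lifestyle effect.** The Appendix C algorithm was run 500 times at N = 300. The severity model, the component correlations and the 12-month change (mean −0.9, SD 1.2) are assumptions. The score was entered as continuous. Time since diagnosis, follow-up time, antidepressant use and rounding were not modelled. Ranges and pairs cover change unrelated and related to severity, in that order.
- LifeHD as written, 12-month cUHDRS, no adjustment: p < 0.05 in 100% of runs. The mean correlation with cUHDRS was 0.82 to 0.83. No lifestyle item was retained in 83 to 85% of runs.
- The same, adjusted for baseline cUHDRS: 5.6 to 8.2%.
- LifeHD as written, 12-month change: 29% and 85% unadjusted; 28% and 35% with baseline adjustment.
- Age, CAG and stage left out of the score, with age, sex and stage adjusted for in Step 1: 5.0 to 5.6% for 12-month cUHDRS; 18% and 16% for 12-month change (no baseline adjustment).

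In the last case about 80% of runs retained no item and were counted as non-significant. The low rate therefore does not show that a derived score is tested at its nominal level.

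**The case against.** A reader might infer that every LifeHD analysis would show a strong association with no lifestyle effect. The SAP does not support that. Section 6.2.2 says unweighted regressions control for age, HD stage and the baseline outcome. Using LifeHD by itself drops the other lifestyle factors; nothing says it drops those covariates. With baseline adjustment, the false signal for 12-month cUHDRS falls close to the nominal level.

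A reader might also take the lifestyle share to be about 1%. That needs 0.23 to be raw cUHDRS points, which the SAP leaves unclear. On a standardised reading the share is several times larger, though still a minority.

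Inclusion of the three measures is open: Table 4 marks them non-modifiable, and Step 5 calls the sum a risk score. A combined prognostic index is a legitimate design. Step 1 already adjusts for age and HD stage. The separate sleep, diet and activity analyses do not depend on LifeHD.

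All of this stands, and it limits the point without removing it. Adjusting for age and HD stage adjusts for parts of the score itself, so the coefficient no longer describes the score as defined, and CAG stays unadjusted. Section 6.2.2 falls back on a mean difference when balance fails, and Appendix C tabulates the correlation of LifeHD with the outcome; neither is stated to adjust for baseline. Open disclosure of the ingredients does not justify the reading in Table 5.

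**Conclusion.** The defect lies in the text: the score's content and its stated interpretation do not match. As planned, LifeHD will mainly reflect disease stage, and it can lose all its lifestyle items through significance selection.

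The spurious association with 12-month cUHDRS applies to results without baseline adjustment, namely the mean-difference fallback and the Appendix C correlations. Elsewhere the harm is chiefly one of interpretation.

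The size rests on assumed TFC midpoints, stage mix and effect scale. From TFC alone, stage contrasts are about 2.9 to 5.3 cUHDRS points, and diet, sleep and activity make up roughly 1 to 19% of the combined variance. The simulation figures depend on an assumed disease model.

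This should be fixed before analysis. It does not threaten the primary feasibility outcomes, and LifeHD is supplementary in a study declared exploratory.

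**What to change.** - In Step 5, sum only the modifiable items. Settle whether antidepressant use is one of them: Table 4 lists it as modifiable, but the list in Section 6.2 omits it.
- Keep age, CAG length, HD stage and the baseline outcome as covariates in Steps 1 and 2 and in every LifeHD outcome model.
- Do not report an unadjusted LifeHD mean difference as a lifestyle effect, and label the tabulated correlations accordingly.
- State what will be reported if no lifestyle item passes Step 1.
- Amend Section 6.2, Table 4 (including its caption) and Table 5 to match.
- If a combined score is also wanted, report it separately as a prognostic index, not as a measure of lifestyle.
- Note that deriving and testing the score on the same data leaves some optimism, which these changes do not remove.

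The cost is SAP wording, and a lifestyle score that will look less predictive. No new data are needed.
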